1.5 Dose Rationale and Risk/Benefits

For children ages 1 to 3 years, the recommended dietary intake (RDI) for choline is 200 mg. and the maximum upper limit for tolerability is 1000 mg. (Food and Nutrition Board - Institute of Medicine, 1998). For children ages 4 to 8 years, the RDI for choline is 250 mg. and the maximum upper limit for tolerability is also 1000 mg. (eating two eggs would provide an equivalent of 545 mg. of choline). The goal of the current study is to provide choline supplementation as opposed to simply ensuring choline sufficiency. Our previous two studies used a fixed 500 mg. dose, regardless of the child's weight

CONFIDENTIAL

This material is the property of the University of Minnesota. Do not disclose or use except as authorized in writing by the study sponsor

(Wozniak et al. 2013, and Wozniak et al., 2015). The dose was well-tolerated, with partial or full doses received on 88% of the 270 days in the study. There was no difference between 500 mg. choline and placebo in terms of doses received or participant drop-out. There were no serious adverse events and no adverse events that differed by group other than fishy body odor in the choline group (an expected adverse event). A substantial proportion of children in the choline group (52%) compared to the control group (4%) did experience fishy body odor at some point in the 9 month study. For the smallest children in the study by weight, nearly 100% experienced fishy body odor at some point.

For the current study, choline will be given at a 19 mg per kg dose, based on evidence from the prior two pilot studies showing increased rates of fishy body odor at higher doses and also on data indicating that memory performance was optimal at doses in the 19 mg per kg range. Choline will be administered in the form of a fruit-flavored drink mix containing choline bitartrate (compounded for the study by Fagron, St. Paul, MN; Investigational New Drug Application #107085). Balchem (New Hampton, NY) manufactures the choline bitartrate to USP standards. The parent will add the powder to plain water. The matching placebo drink mix (without choline bitartrate) will also be provided by Fagron. Material will be stored, labeled, allocated, and dispensed by the University of Minnesota's Investigational Drug Service (IDS) Pharmacy.

Participant families will be given a 65 day supply initially. Re-supply will be handled by packages mailed after the investigators have verified the participant's continued involvement in the study and freedom from serious adverse events during telephone visits. The preparation, coding, and tracking will be handled by the University of Minnesota's Investigational Drug Service pharmacy.

Choline is considered a GRAS substance (generally regarded as safe) by the FDA and the dose to be utilized in this study is lower than the maximum tolerable upper limit. Based on our previous study, tolerability for this lower dose of choline is expected to be high. Parents will be educated at the time of enrollment about potential side effects of choline which rarely occur and usually at much higher doses than those proposed (hypotension has been reported at 7.5 grams per day; gastrointestinal symptoms (loss of appetite, upset stomach), sweating, or body odor have occurred at 10-16 grams per day). As indicated, in the first 60 participants, we only observed fishy body odor and not other adverse events.

At one month, a full range of potential side effects will be screened. Although allergic reactions to choline are not expected (we observed none in the pilot studies), we will monitor for a range of allergic symptoms nonetheless. Adverse events and serious adverse events will be reported to the University of Minnesota IRB and to Quorum IRB. Serious adverse events will also be reported to the NIH program officer.

CONFIDENTIAL

This material is the property of the University of Minnesota. Do not disclose or use except as authorized in writing by the study sponsor

2. Study Objectives

Primary Objective

Evaluate the efficacy of choline in treating memory deficits and executive functioning deficits in children with FASD.

Secondary Objectives

Evaluate the long-term effects of choline supplementation by re-assessing children who took choline and placebo as part of the previous pilot study.

Evaluate the potential interaction between genotype ((for example PEMT, rs12325817) and response to choline intervention.

3. Study Design

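### Section 1.5 describes body odor to parents as a rare, gram-dose effect, yet reports it in 52% of pilot children given choline at 500 mg a day

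*Combined protocol and SAP*

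**What the plan says.** Section 1.5 (Dose Rationale and Risk/Benefits) treats side effects twice.

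The account of the two pilot studies comes first. "Our previous two studies used a fixed 500 mg. dose", whatever the child's weight. On adverse events, the pilots had "no adverse events that differed by group other than fishy body odor in the choline group", and the text labels odor as expected. It then gives the rate: "A substantial proportion of children in the choline group (52%) compared to the control group (4%) did experience fishy body odor" at some point over nine months, and close to 100% among the lightest children. Odor is also one of the stated reasons for moving to weight-based dosing.

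Later in the section, the subject is what parents will be taught at enrolment: "potential side effects of choline which rarely occur and usually at much higher doses than those proposed". In the list that follows, sweating and "body odor have occurred at 10-16 grams per day". The next sentence turns back to the pilots: "in the first 60 participants, we only observed fishy body odor and not other adverse events".

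Section 3.4, which summarizes the risks, covers hypotension, gastrointestinal symptoms and allergy. It does not mention odor. It describes the present doses as no higher than those of the pilots. The Study Summary gives 19 mg/kg, typically 200 to 425 mg, with a maximum of 500 mg.

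**The concern.** Odor is the only adverse event that the trial's own data tie to choline, and it was seen at a dose that is the ceiling of the present one. The sentence on parent education puts it among effects that are uncommon and belong mostly to far larger doses. If parents are taught that, they are consenting for children aged 2.5 to 5 on a wrong idea of how often the effect occurs and at what dose. Section 11 requires the consent form to give enough information for an informed decision, so the protocol's description of what parents learn should agree with its data.

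The sentence on other adverse events has a separate fault. That no other event differed between arms is a statement about a comparison. That no other event was observed is a statement about counts, and a much stronger one.

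**Working it through.** **1. The statements side by side (all in section 1.5 unless noted).**

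| Point | Pilot account | Parent education and the sentence after it |
|---|---|---|
| Frequency of odor | 52% choline v 4% control; nearly 100% in the smallest children | side effects occur rarely |
| Dose | 500 mg/day | body odor listed at 10–16 g/day |
| Status | expected adverse event | seen in the first 60 children, no rate given |
| Other adverse events | none that differed by group | none observed |

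**2. Dose ratios.**
- Gram doses against the pilot dose: 10 / 0.5 = 20 and 16 / 0.5 = 32.
- Gram doses against this trial's 200–500 mg: 10,000 / 500 = 20 up to 16,000 / 200 = 80.
- Pilot dose against this trial's typical range: 500 / 425 = 1.2 up to 500 / 200 = 2.5. At the 500 mg maximum the ratio is 1.

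**3. The same comparison per kilogram.** Weight = dose / 19 mg/kg, so 200, 425 and 500 mg correspond to about 10.5, 22.4 and 26.3 kg. At those weights the fixed pilot dose was 47.5, 22.4 and 19 mg/kg. The present dose is therefore 19 / 47.5 = 0.4 to 19 / 19 = 1.0 times the pilot dose. It lies close to the dose with the 52% rate and far from the gram doses.

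**4. Could 52% be a small-sample accident?** The documents give no counts, so the percentages cannot be reproduced. As an assumption, take every pair of whole-number counts that rounds to 52% and 4%, with 15 to 45 children per arm and 40 to 60 in total. There are 41 such pairs. Fisher's exact test gives a two-sided p of at most 0.0007 in all of them. The lower 95% Clopper-Pearson limit for the choline arm lies between about 30% and 34%. With a total of exactly 60, the only pair is 17/33 against 1/27. Under none of these does the pilot rate fit the word rarely.

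**5. Other adverse events.** The pilot account supports only that nothing but odor differed by group. Section 3.4 makes a claim of the same kind for gastrointestinal symptoms: no significant increase. Neither says that none occurred. The definition in section 8.1.1 counts intercurrent illness, so a literal absence of other events in 60 young children over nine months would be a striking result. Whether the pilots used that definition is not stated.

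**The case against.** The best defense is that the education sentence describes the topic for readers of the protocol and is not a script for parents. It is hedged by the word usually, it reports where effects have been seen without claiming a threshold, and the next sentence refers back to odor in the pilots. Nothing is hidden from an ethics board that reads the whole section. Part of this stands. The consent text is not available, so what parents are actually told cannot be checked. But the sentence describes an enrolment procedure, and the follow-on sentence gives no rate and does not withdraw the word rarely.

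Three stronger readings are tempting, and the documents do not support them.

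- **Differential withdrawal.** A reader might infer that parents surprised by odor would stop the drink or leave, mostly in the choline arm. Section 1.5 reports no pilot difference between arms in doses received or drop-out despite 52% v 4%. What pilot parents were told is unknown, so this is not decisive, but it is the only evidence on the matter. Sections 5.5 and 6.2 also provide frequent contact about adverse events and compliance.
- **A forecast for this trial.** A reader might carry 52% over to the present choline arm. Most children would receive less than the pilot dose, and the documents project no odor rate at 19 mg/kg.
- **A misled monitoring board.** Under section 8.6.1 the board receives adverse event counts by treatment arm, so its judgment does not depend on the background sentence in 1.5.

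**Conclusion.** Section 1.5 contradicts itself on the frequency and dose of body odor, and it overstates the pilot finding on other adverse events. On the first point, an effect described as rare and listed at 10–16 g/day was seen in 52% of choline children at a dose 20 to 32 times lower. The comparison of statements and the dose ratios rest on the documents alone. Only the exact test and confidence limits rest on assumed counts, and the conclusion does not need them.

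The consequence is for the accuracy of what parents learn before consenting. The design, sample size and analysis are unaffected. No view is taken on the dose or on when treatment should stop.

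**What to change.** - **Section 1.5, parent education.** Reconcile it with the pilot account. Describe fishy body odor as a common and expected effect in the pilots at 500 mg (52% v 4%), more frequent in lighter children, and say that the rate at the present dose is not yet known. If the parent materials carry the same wording, change them to match.
- **Section 1.5, pilot summary.** Replace the statement that no other adverse events were observed with one that no other adverse event differed by group.
- **Section 3.4.** Name odor in the risk summary.

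The cost is a few sentences and an ethics-board submission. There is one real downside: parents in both arms may watch for odor and guess the assignment, which matters because the Child Behavior Checklist (section 3.3) is caregiver-rated. That risk already exists with an effect this visible. It is a reason to word the information identically for all families and not a reason to leave the contradiction in place.

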3.1 General Design

This is a randomized, double-blind, placebo-controlled study. Sixty children, male and female, between the ages of 2 years and 5 years at enrollment will be included.

Eligible participants will be randomized to treatment or placebo in a 1:1 allocation ratio. A block randomization procedure with variable block sizes will be used to maximize unpredictability of assignment.

Participants will receive the test article for nine months and will have an in-person baseline visit followed by 11 additional visits (9 telephone visits; 2 additional in-person visits) for a total of 12 visits. A telephone visit for purposes of safety and compliance will occur at 2 weeks. A telephone visit will be scheduled for 1 month after administration of the test article begins. Formal complete follow-up assessments will occur at 6 months and 9 months. Telephone visits for safety and compliance will occur at months 2, 3, 4, 5, 7, 8 and 10. Parent-report measures of behavior will be collected. Behavioral paradigms will be used to assess memory and other cognitive functions. Formal psychometric testing to establish developmental levels will be completed. Blood will be collected to assess compliance with the treatment and effect on blood choline levels. DNA will also be extracted for analysis of single nucleotide polymorphisms related to endogenous choline production. Plasma will also be analyzed for immune function and micro-RNA.

As part of the project, participants from the previous study (1R21AA019580 / 4R33AA019580) will be brought back to the University for a set of cognitive evaluations to assess the long-term effects of having taken choline/placebo previously.

3.2 Primary Study Endpoints

The primary study endpoints will be cognitive assessments. These will include the Elicited Imitation memory task and the Stanford-Binet Intelligence Scales.

CONFIDENTIAL

This material is the property of the University of Minnesota. Do not disclose or use except as authorized in writing by the study sponsor

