5.7 Packaging

The test article, a powdered drink mix, will be packaged in individual foil packets. The powdered drink mix in each foil pack will contain either choline bitartrate or placebo. The test article will be delivered by courier from the manufacturer (Fagron) to the

CONFIDENTIAL

This material is the property of the University of Minnesota. Do not disclose or use except as authorized in writing by the study sponsor

University of Minnesota Investigational Drug Service where the labels will be prepared and where the material will be kept prior to distribution to research participants. Each foil packet will be labeled with a study number, date of manufacture, a code by which the contents (choline bitartrate vs. placebo) can be tracked, cautionary note, and indication of "investigational drug" status.

5.8 *Blinding of Study Drug*

Each packet of test article will be coded with an arbitrary code number. The University of Minnesota Investigational Drug Service will keep the link between these codes and the contents (choline bitartrate vs. placebo). The investigators will remain blinded throughout the study. The study statistician, [name], will have access to the link and, therefore, will be unblinded.

5.9 *Receiving, Storage, Dispensing and Return*

5.9.1 *Receipt of Drug Supplies*

Balchem, the manufacturer of the active agent and the placebo, will ship the product to a compounding pharmacy (Fagron). The transportation and packaging will take place according to GMP (good manufacturing practices). Fagron will then ship the material in sealed foil packets to the University of Minnesota Investigational Drug Service (IDS). IDS will perform an inventory, complete a drug receipt log, and return any damaged material to the manufacturer. This will be documented and the study sponsor will be notified. There are no special storage requirements for this product.

5.9.2 *Dispensing of Study Drug*

The Investigational Drug Service will assign the test article (choline bitartrate or placebo) to each participant by consulting the randomization schedule. The investigators will pick up the coded test article from the IDS in several amounts. Initially, 30 packets will be distributed to participating family at the study baseline visit. The remaining material will be distributed in batches of 60 packets.

The investigator will keep a log onsite to ensure all medication that is dispensed is recorded the day of the baseline visit and the days of shipment.

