6.1 Visits 1, 8, & 11 (Baseline and follow-up assessment visits)

Participants and their parent/guardians identified as described in Section 4.3 of this protocol will be asked to come for a baseline visit (Visit 1). This visit is expected to last for approximately 3 to 3.5 hours. Visits 8 and 11 will be similar, but slightly shorter (2.5 to 3 hours) because several tasks are not repeated. The following procedures will occur:

- Consenting process (Visit 1 only);
- Medical history (Visit 1 only) and physical exam
- Concomitant medications will be recorded
- Height
- Weight
- Head circumference
- Facial photograph to allow for detailed measurements (Visit 1 only)
- Blood pressure
- Blood collection for choline and metabolite (betaine, phosphatidylcholine, sphingomyelin, and trimethylamine-N-oxide (TMAO) level (3 ml tube).
- Plasma extracted from this whole blood will be analyzed for measures of immune function (cytokines) and micro-RNA..
- Extraction of DNA sample from any blood sample for single nucleotide polymorphisms related to endogenous choline synthesis (PEMT rs12325817)
- Astley & Clarren's FASD diagnostic evaluation including a photograph of the child's face for computer measurement and analysis (Visit 1 or Visit3)
- Stanford Binet Intelligence Scales, Fifth Edition (Visit 1 and 11 only)
- Elicited Imitation Paradigm, including video-recording to facilitate scoring afterward
- Minnesota EF Scale (MEFS), Early Childhood Version
- NIH Toolbox Flanker Inhibitory Control and Attention Task
- Beery Developmental Test of Visual-Motor Integration (VMI) (any visit)
- Scales of Independent Behavior (SIB) (any visit)
- Child behavioral questionnaires (CBCL); a parent-report instrument
- 24-hour Diet interview (for the parent/guardian to complete about the subject)
- Child Eating Behavior Questionnaire (CEBQ); a parent-report instrument
- Randomization (Visit 1 only)
- Training on how to store, mix, and administer the study medication (Visit 1 only)
- Adverse events will be recorded (Visits 8 & 11 only)
- Dispense a supply of the test article (30 packages at Visit 1)
- Provide instructions for returning for the next follow-up visit (Visits 1 & 8 only)

6.2 Visits 2, 3, 4, 5, 6, 7, 9, 10 & 12 (compliance/safety phonecontacts)

At each of these visits, study staff will place a phone call to the participant's parent/guardian. The following information will be collected:

CONFIDENTIAL

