7.1 Sample Size Determination

For purposes of sample size determination, the dependent measure was the percent of correct items on delayed recall of the EI task (averaged across two events per timepoint). The effect size from our completed trial was $d=0.66$. A power analysis was carried out using Optimal Design Software for Multi-level and Longitudinal Research (Version 3.01) to determine the sample size that would be necessary to detect a difference in linear change between treatment and placebo groups with this effect size (Feingold 2009). The analysis assumed that the data would be analyzed using a mixed models repeated measures design for a person-randomized trial, with an effect size $d=.66$, and a two-tailed type I error of 0.05. To achieve 80% power, a sample size of 58.5 participants (approximately 30 per treatment arm) is necessary. This is consistent with the significant group difference that was observed in the pilot trial. The sample size for the proposed study will therefore be fixed at 60 children. Combining participant data

CONFIDENTIAL

This material is the property of the University of Minnesota. Do not disclose or use except as authorized in writing by the study sponsor

for some outcome measures from the first set of pilot studies (N=60) and the proposed study (N=60) will provide additional power to further evaluate age, sex, and PEMT genotype as moderating variables.

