7.2 Statistical Methods

Statistical analyses will utilize an Intention to Treat (ITT) approach. Mixed models analyses with growth curve estimates will form the basis of the core analyses.

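### Two unranked primary endpoints with no stated success rule, while the 5% error and 80% power in Section 7.1 belong to Elicited Imitation delayed recall alone

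*Combined protocol and SAP*

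**What the plan says.** Section 3.2 introduces the primary endpoints as cognitive assessments and continues: "These will include the Elicited Imitation memory task and the Stanford-Binet Intelligence Scales". It names no score and does not order the two instruments.

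Section 7.1 gives a score and a contrast for one of them. "For purposes of sample size determination, the dependent measure was the percent of correct items on delayed recall of the EI task", averaged over two events per timepoint, and the aim was to "detect a difference in linear change between treatment and placebo groups". The effect size is d = 0.66, taken from the earlier trial, with 1:1 allocation under Section 3.1. The error rate is stated ("and a two-tailed type I error of 0.05") and so is the result ("To achieve 80% power, a sample size of 58.5 participants"), which is then fixed at 60 children.

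Section 7.2 has two sentences. One adopts intention to treat; the other reads: "Mixed models analyses with growth curve estimates will form the basis of the core analyses". Section 7.3, on analysis populations, is marked not applicable. Section 6.1 schedules EI at Visits 1, 8 and 11 (baseline, 6 and 9 months), but SB at Visits 1 and 11 only.

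No section ranks the two endpoints, divides alpha, says whether one or both must succeed, names the SB score, or gives a power figure for SB.

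**The concern.** The plan states an error rate but does not define the claim to which it applies. Section 7.1 limits its choice of EI delayed recall to sample size determination, so it hints at a lead endpoint without declaring one. Section 3.2 calls SB primary on equal terms.

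Three readings are open: EI leads, either endpoint suffices, or both are required. Under the first, the figures in 7.1 stand for the primary claim. Under the second, the error rate exceeds 5%. Under the third, error is controlled but the 80% no longer describes the chance of success. With no rule fixed in advance, the reading could be chosen after the results are known, and a significant SB result beside a non-significant EI result (or the reverse) would have no agreed interpretation.

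**Working it through.** **Inputs from the documents.** d = 0.66, two-tailed alpha 0.05, power 80%, required N 58.5, planned N 60 (all Section 7.1); 1:1 allocation (3.1); EI at three visits and SB at two (6.1).

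**Assumptions.** The documents give neither the correlation r between the two test statistics nor an SB effect size. I use r from 0 to 0.9, bivariate normal statistics and, where needed, an SB noncentrality equal to that of EI.

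**1. The plan's own figure.** A plain two-group comparison needs N = 4 × (1.960 + 0.842)² / 0.66² = 72.1 before rounding, or 74 at 37 per arm. The stated 58.5 is smaller by the factor 58.5 / 72.1 = 0.81. A repeated-measures analysis can supply that: a baseline-adjusted comparison needs a correlation of about 0.43, since 1 − 0.43² ≈ 0.81; a slope over 0, 6 and 9 months under compound symmetry needs about 0.58. Section 7.1 gives no correlation or variance component, so 58.5 is neither reproduced nor shown to be wrong. Steps 3 and 4 accept it; step 5 shows what happens if it is optimistic.

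**2. Either endpoint counts, each at 0.05, no true effect on either.** Error = 1 − P(|Z1| < 1.96 and |Z2| < 1.96). At r = 0 this is 1 − 0.95² = 0.0975. For any r it is at most 0.05 + 0.05 = 0.10.

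**3. Both required at N = 60.** Noncentrality = (1.960 + 0.842) × √(60 / 58.5) = 2.837, so EI power is Φ(2.837 − 1.960) = 0.810. Joint power cannot exceed this. With equal noncentrality for SB and r = 0, it is 0.810² = 0.656.

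**4. Fixed sequence, EI then SB, each at 0.05.** If neither endpoint has an effect, an error requires EI to be falsely significant, so the rate is 5.0%. If EI has its planned effect and SB has none, the rate at r = 0 is 0.810 × 0.05 = 0.0405, and it falls as r rises. EI power stays at 81%.

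| Assumed r | Either at 0.05: error | Both required: power | Fixed sequence: error, EI effective and SB null |
|---|---|---|---|
| 0 | 9.75% | 65.6% | 4.05% |
| 0.5 | 9.1% | 70.1% | 3.4% |
| 0.7 | 8.3% | 72.6% | 2.9% |
| 0.9 | 7.0% | 76.1% | 2.5% |

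**5. Sensitivity of the power figures.** With the plain two-group comparison and 30 per arm, noncentrality is 0.66 / √(2/30) = 2.556. EI power is then 72%, and both-required power is 52% (r = 0) to 66% (r = 0.9). Separately, SB has two assessments against EI's three. Under compound symmetry the variance of the 9-month change is proportional to 81/42 = 1.93 for EI and 81/40.5 = 2 for SB. SB noncentrality becomes 2.837 × √(1.93/2) = 2.786, and both-required power at r = 0 becomes 64% instead of 66%. That difference is minor.

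**The case against.** The best defence is that EI is evidently the lead endpoint. It is the only one sized, and if it leads, or if both endpoints are required, the primary claim stays within 5%. This part stands: the excess error belongs to one of three readings. A reader might infer that the trial as planned has a false-positive rate near 10%. The documents do not support that, because they nowhere say that either endpoint suffices. Nor do they say that EI leads, so the gap remains.

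Two other strong readings also go too far:

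- The phrasing of 3.2 could be taken as an open list that leaves room for further primaries. Section 3.3 introduces the secondary endpoints in the same way, exactly two primary instruments are named, and no third appears elsewhere. It is as likely to be house style.
- It could be said that SB has no contrast at all. The Study Summary applies growth-curve analysis to the outcome measures, 7.2 makes it the core method, and with two SB visits a linear growth term is the change from Visit 1 to Visit 11. That contrast is reasonably implied. The score, its power and the success rule are what is missing.

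The trial is also small, labelled Phase I and II, and its Study Summary gives feasibility and tolerability as the objective. This lowers the severity but does not remove the point: Section 2 makes efficacy the primary objective, and 7.1 sets a formal two-tailed error rate.

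Finally, testing EI first is one cure among several, and the choice belongs to the sponsor.

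**Conclusion.** The omission is real and should be fixed. Two primaries are named without ranking, the stated alpha and power attach to one EI score, and no success rule or SB score is given.

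Its size depends on the reading. Under an either-endpoint rule, error is 9.75% with independent tests, about 7% to 9% at assumed correlations of 0.9 to 0.5, and at most 10% whatever the correlation. Under a both-required rule, power cannot exceed that for EI alone. It is about 66% to 76% at N = 60 if 58.5 is accepted and SB has the same standardised effect and precision, and lower if 58.5 is optimistic. If EI leads, nothing is lost beyond the missing statement.

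The conclusion does not depend on whether 58.5 is correct. A reader might take the failure to reproduce it as proof of an error, but the inputs for the mixed-model calculation are not given, so the documents do not support that.

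**What to change.** **Section 7.2.** State that EI delayed-recall percent correct (treatment difference in linear change over Visits 1, 8 and 11) is tested first at two-sided 0.05. One SB score, named by the sponsor (treatment difference in change from Visit 1 to Visit 11), is tested at two-sided 0.05 as confirmatory only if EI is significant. Naming EI as sole primary and SB as secondary would serve equally well. Splitting alpha at 0.025 each would also control error, but on the plan's own basis EI power at N = 60 falls from 81% to 72%, and about 71 children would be needed to restore 80%.

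**Section 7.1.** State that the 80% power applies to EI only.

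**Who and when.** Section 5.8 says the study statistician "will have access to the link and, therefore, will be unblinded", so blinded staff should fix the rule, in a dated amendment, before any efficacy data are examined by arm. The report contents listed in 8.6.1 are accrual, drop-outs, losses to follow-up and adverse event counts, which include no efficacy results. The same section says the board reviews unblinded data, so the sponsor should confirm that no efficacy data have been seen by arm. If they have, report SB as secondary and show both results.

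**Related point.** Section 2 includes executive functioning in the primary objective, while 3.3 lists the Minnesota Executive Functioning Scale and the Flanker task as secondary. The sponsor should reconcile these in the same amendment.

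**Cost.** Wording only: no new data, and no change to N or to EI's alpha and power. SB can be claimed only after EI succeeds. If SB had the same effect and precision as EI, its chance of being claimed would be 66% to 76%, against 81% if tested alone at 0.05.
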